Therefore, if our study is successful in implementing a sustainable evidence-based dietary program, the next step will be to establish a specialized nutritional prenatal care service designed to prevent clinical complications and improve pregnancy outcomes. This will involve

increasing the dedicated time and frequency of comprehensive dietary counseling sessions during gestation. These sessions will be independent from routine prenatal care visits. In addition, we plan to work with local government and private healthy diet organizations to help socially vulnerable pregnant women overcome nutritional challenges.

Objectives and Hypothesis

Primary Objective

To examine the feasibility and adherence to a MedDiet program initiated in the first or early second trimester of gestation (6-16 weeks) among overweight and obese women.

Hypothesis: Overweight and obese pregnant women enrolled in the MedDiet program have an elevated level of adherence facilitated by the design of a comprehensive dietary program with free home-delivered meals, nuts, and EVOO bottles. This hypothesis will be tested by examining adherence to the MedDiet program using a validated screening tool.³⁹

Secondary Objectives

1. To estimate the preliminary efficacy of a MedDiet intervention controlling gestational weight gain and reducing adverse pregnancy outcomes (APO).

Hypothesis: Overweight or obese pregnant women consuming MedDiet have low rates of excessive gestational weight gain and adverse pregnancy outcomes. This hypothesis will be tested by comparing gestational weight gain and pre-selected pregnancy outcomes between women allocated in each dietary group.

2. To estimate the preliminary impact of MedDiet intervention on maternal cardiometabolic profile.

Hypothesis: MedDiet leads to favorable effects on cardiovascular clinical parameters and cardiometabolic biomarkers in pregnancy. This hypothesis will be tested by comparing maternal cardiovascular parameters trends and cardiometabolic biomarkers during pregnancy among the studied groups.

Methods and Measures

Study Design

Type of study

This is a prospective, randomized, pilot study with a behavioral intervention. Sixty participants diagnosed as overweight ($BMI 25.0-29.9 \text{ kg/m}^2$) or obese ($BMI \geq 30.0 \text{ kg/m}^2$) in the first or early second trimester of gestation will be invited to participate.

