- Following informed consent and eligibility confirmation, subjects will be randomized in blocks of 4 using a single sequence computer-generated random number⁴⁰ to balance for baseline BMI category (overweight or obese Random allocation number assigned to MedDiet program (intervention group) or ACOG-based nutritional counseling (control group) will be in a sealed opaque envelope.
 - Subjects allocated to the ACOG-based Dietary Program (Control Group) will receive:
 - Following ACOG recommendation, routine counseling on healthy eating will be provided. This will include advice on the consumption of grains, fruits, vegetables, protein, and dairy foods recommended during pregnancy ([Nutrition During Pregnancy | ACOG](#))⁴¹ (www.myplate.gov). (Appendix A-F (English)/Appendix G-L (Spanish))
 - Diet adherence will be assessed using a Routine Diet Adherence Questionnaire (Appendix M (English)/Appendix N (Spanish)).
 - Six traditional healthy meals will be shipped by ModifyHealth LLC directly to the participant's home every 3 weeks between enrollment and until the subject is approximately 38 weeks pregnant.
 - Participants will receive canola oil and a healthy snack during their enrollment visit and during their routine 26-30 week prenatal visit
 - Subjects allocated to the MedDiet Program (Intervention Group) group will receive:
 - Counseling based on the principles of the traditional MedDiet²⁷ with a focus on a general change in diet instead of micronutrients or macronutrients. (Appendix O-P;SS-UU (English)/Appendix Q-R; VV-XX (Spanish))
 - Diet adherence will be assessed using a modified version of the validated MedDiet Adherence Questionnaire.³⁹ (Appendix S (English)/Appendix T (Spanish))
 - Six traditional MedDiet meals will be shipped by ModifyHealth LLC directly to the participant's home every 3 weeks between enrollment and until the subject is approximately 38 weeks pregnant.
 - Participants will receive olive oil and nuts during their enrollment visit and during their routine 26-30 week prenatal visit.

Baseline Visit:

- All subjects will participate in a 30-minute baseline Nutritional Assessment and Diet Counseling Session regardless of the arm they are randomized to. This will occur during their initial prenatal visit at 6-16 weeks of pregnancy. The following items will be covered in this visit:

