 - Subjects will complete an enrollment questionnaire to obtain demographic and baseline diet/physical activity information (Appendix U (English)/Appendix V (Spanish))
 - Subjects will complete a form for ModifyHealth so their free meals will be delivered to their home (Appendix VV (Spanish)/ Appendix WW (English))
 - Additional subject enrollment data will be collected by the enrolling research teammate regarding a history of eating disorders, tobacco/alcohol/substance use, insurance coverage, phone number, and email (Appendix W(Spanish)/Appendix SS (English)).
 - Subjects will complete the Federation of Gynecology and Obstetrics (FIGO)⁴² Nutrition Checklist (Appendix X (English)/Appendix Y (Spanish)). This is a validated tool used to assess the subject's quality of diet. It consists of six yes/no questions (www.figo.org) and at least one "no" response will be classified as a suboptimal diet.⁴²
 - All subjects will have a total of 8 ml of blood drawn for the following tests:
 - C-reactive protein (CRP) panel
 - metabolic panel that includes glucose level
 - the lipid panel
 - hemoglobin A1c

The blood sample collection form will be completed at each timepoint (Appendix Z)

- All subjects will receive dietary advice for the diet they have been randomized to by a registered dietitian with expertise in nutrition during pregnancy (ST, Co-I). (Appendix A-C; F (English)/Appendix G-;-L (Spanish) or Appendix O-P (English)/Appendix Q-R (Spanish))
 - Educational materials for each diet program such as recipes, shopping lists, and meal plans will be discussed, and the material will be printed for the participant's use at home. (Appendix A-F (English)/Appendix G-L (Spanish) or Appendix O-P; SS (English)/Appendix Q-R; VV (Spanish))
 - Routine counseling of physical activity and exercise based on ACOG recommendations (ACOG Committee Opinion No 804) will be provided. If there are no clinical contraindications, women will be encouraged to start with low intensity, short periods of exercise at least 4 times a week. (Appendix A-F (English)/Appendix G-L (Spanish) or Appendix O-P (English)/Appendix Q-R (Spanish))

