- All subjects will be screened for household food insecurity, as well as, reliable transportation, housing, and a support system using the standard OB Social Worker Assessment questionnaire which all patients complete as part of their routine care (Appendix AA (English)/Appendix BB (Spanish)).⁴³ Women who screen positive for household food insecurity will be excluded from the study and referred to our clinic

- social worker or registered dietitian for information on community resource assistance such as Loaves and Fishes, a Charlotte-based food bank.
- Participants will be counseled to control gestational weight gain (GWG) following the Institute of Medicine (IOM) recommendations:
 - Total GWG of 15-25 lb. for overweight women (BMI 25.0-29.9 kg/m²)
 - Total GWG Of 11-20 lb. for obese women (BMI \geq 30.0 kg/m²).¹⁰

Trimester Visits:

- An additional ~20-minute in-person, virtual, or phone call dietary counseling sessions will be scheduled at the following time points (Figure 1).
 - Between 20-24 weeks of pregnancy
 - Between 26-30 weeks of pregnancy
 - Between 34-38 weeks of pregnancy

These sessions will include the following:

- The following questionnaires will be completed:
 - Routine Healthy Diet Assessment Questionnaire ((Appendix M (English)/Appendix N (Spanish)) or the MedDiet Assessment Questionnaire (Appendix S (English)/Appendix T (Spanish)))
 - Diet and Physical Activity Recall (Appendix CC (English)/Appendix DD (Spanish))
 - Trimester Collection Form (Appendix EE-GG)
- Education and reinforcement of diet recommendations will be provided by addressing the subjects' questions and issues.
- Subjects will receive recipes specific for the ACOG Routine Healthy Diet ((Appendix D-E (English)/Appendix J-K (Spanish)) or the MedDiet ((Appendix TT-UU (English)/ Appendix WW-XX (Spanish))). Recipes will either be printed for the subjects or sent via EPIC
- If no clinical contraindications were established during the baseline visit, subjects will be encouraged to gradually increase their length and intensity of physical activity and exercise as tolerated from the first trimester until delivery. This will be based on ACOG recommendations.⁴⁴
- Participants will continue to be counseled to control gestational weight gain following the IOM recommendations:
 - Total GWG of 15-25 lbs for overweight women (BMI 25.0-29.9 kg/m²)
 - Total GWG of 11-20 lb. for obese women (BMI \geq 30.0 kg/m²).¹⁰
- The time length for all sessions will be recorded.

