- Between 26-30 weeks, all subjects will have a total of 8 ml of blood drawn for the following tests:
 - C-reactive protein (CRP)
 - metabolic panel that includes glucose level
 - the lipid panel (total cholesterol, triglycerides, high-density lipoprotein (HDL) cholesterol, and low-density lipoprotein (LDL) cholesterol)
 - hemoglobin A1c

The blood sample collection form will be completed at each timepoint (Appendix Z)

- For each meal received from ModifyHealth, subjects will be asked to take share a photo (via REDCap using the subject's cell phone number or email, EPIC, or in-person) of the uneaten food.

Data on subjects' history and pregnancy/neonatal outcomes will be collected via EPIC:

- The following data will be collected from EPIC for all subjects
 - Medical history (Appendix HH (Spanish)/Appendix TT(English)))
 - Reproductive, and obstetric history including all prior pregnancy complications/outcomes and neonate outcomes (Appendix II (Spanish)/Appendix UU(English)))
 - Current pregnancy labs (Appendix JJ)
 - Current pregnancy, scans, complications, progress reports, clinic reports, hospital reports
 - Current pregnancy outcomes (Appendix KK)
 - Neonatal outcomes will be collected up to 6-weeks post-delivery including all birth data and complications (Appendix LL)
- Data regarding any adverse events will be collected on the Adverse Event form. (Appendix MM).
- Data collected on data collection forms (Appendix HH-LL) and then transferred to REDCap.

Fig 1. Overview and Intervention

[figure not shown]

Table 3

	Screening/ Enrollment/ Randomization		Between 20-24 weeks of pregnancy		Between 26-30 weeks of pregnancy		Between 34-38 weeks of pregnancy	
	Routine Diet	MedDiet	Routine Diet	MedDiet	Routine Diet	MedDiet	Routine Diet	MedDiet
Informed consent	X	X						
Inclusion/ Exclusion criteria	X	X						
Medical record release	X	X						
Medical, reproductive, & obstetric history*	X	X						

Nutrition (FIGO) checklist	X	X						
Food insecurity screening	X	X						
Diet information & handouts provided	X	X						
Diet and physical activity counseling	X	X	X	X	X	X	X	X
Blood draw for: 1. CRP 2. metabolic panel 3. Lipid panel 4. A1C	X	X			X	X		
MedDiet adherence screening				X		X		X
Routine Diet adherence screening			X		X		X	
6 meals delivered every 3 weeks	X	X	X	X	X	X	X	X
Olive oil and nuts provided		X				X		
Canola oil and healthy snack provided	X				X			
Exercise/food recall and general assessment questionnaire			X	X	X	X	X	X

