Pregnancy data collected*	X	X	X	X	X	X	X	X
Delivery data collected**								
Neonatal data collected**								

*Data will be collected through medical records

**Data will be collected at 6 weeks post-delivery through medical records.

Outcomes

- **Diet Adherence Assessment:** Adherence of both groups will be assessed with a questionnaire based on a validated diet adherence questionnaire³⁹ during counseling sessions as described above. Questionnaires will be scored with a “1” assigned to all responses corresponding to the recommended guidelines and a “0” assigned to all responses which do not correspond to the recommended guidelines. The level of adherence will be defined based on the scale score as: ≤4 low adherence, 5-11 moderate adherence, and ≥ 12 high adherence.
- **GWG:** Total GWG will be calculated by subtracting the participant’s weight (lbs.) at the initial prenatal visit from the weight (lbs.) at time of the delivery or at the last prenatal visit. GWG in the first trimester (6-13 weeks), second trimester (14-26 weeks), and third trimester (27-40 weeks) will also be calculated. Calibrated weight scales will be used at our clinic and at the hospital. Compliance rate of GWG based on IOM guidelines for overweight and obese women¹⁰ will be compared between the MedDiet and the control group.
- **Adverse Pregnancy Outcomes (APO):** We will examine the most common Adverse Pregnancy Outcomes (APO) associated with overweight and obesity (Table 3).^{2,4,5-7,45-51} Definition and management of all APO will follow the standardized guidelines at Myers Park OBGYN clinic.

Table 3 Adverse Pregnancy Outcomes (APO)

APO	Prevalence in Pregnant Women
HDP (preeclampsia, eclampsia, or gestational hypertension)	4-6% of overweight/obese women BMI ≥30 ⁴⁵ 12% in women with a BMI ≥40 ⁴⁶
GDM	6-14% in overweight/obese women ⁴⁷
PTB	10.2% in US in 2021 was 10.2% (www.cdc.gov); data suggest increased risk among overweight/obese women 48-50
Cesarean Delivery	29.9% in NC in 2020 (www.cdc.gov); There is a dose-response relationship between pre-pregnancy BMI and cesarean delivery rate. ^{4,7,51}
Large for Gestational Age (LGA) infant	Data suggestion relationship between LGA (birth weight >90th percentile) and overweight /obese women ^{7,51}

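### MedDiet adherence is scored only in the MedDiet arm and only from 20-24 weeks, so the pilot can describe a level but cannot show that the program raised it

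*Combined protocol and SAP*

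**What the plan says.** The primary objective is feasibility of, and adherence to, the MedDiet program. Its hypothesis expects a raised level of adherence and credits the program's design for it. On the test, the Primary Objective text says: "This hypothesis will be tested by examining adherence to the MedDiet program using a validated screening tool".

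Under Randomization and Study Groups each arm has its own instrument. For controls, "Diet adherence will be assessed using a Routine Diet Adherence Questionnaire" (Appendix M/N). For the MedDiet arm, "Diet adherence will be assessed using a modified version of the validated MedDiet Adherence Questionnaire" (Appendix S/T). Trimester Visits offers the two forms as alternatives at 20-24, 26-30 and 34-38 weeks. In the schedule of activities (the first of two tables numbered 3), the row "MedDiet adherence screening" is marked only in the MedDiet columns at those three sessions. The corresponding routine-diet row is marked only in the control columns. Neither is marked at enrollment.

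Outcomes, Diet Adherence Assessment, then treats the arms together: "Adherence of both groups will be assessed with a questionnaire based on a validated diet adherence" questionnaire, as already described, with one set of cut-offs, "≤4 low adherence, 5-11 moderate adherence, and ≥ 12 high adherence".

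Other diet data are collected in both arms. At baseline, "Subjects will complete an enrollment questionnaire to obtain demographic and baseline diet/physical activity information", and all women complete the six-item FIGO checklist. A diet and activity recall is completed at the three later sessions, and women are asked for photos of uneaten food from delivered meals. Neither Outcomes nor the Analytical Plan gives any of these an adherence score or a role in the adherence outcome.

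**The concern.** To say that adherence is raised needs a reference level, and to credit the program needs a contrast. On the MedDiet scale the plan collects neither. A level first measured weeks after counselling and food supply begin cannot be separated from what the women already ate. Nor can it be separated from what the control arm, which also receives counselling, meals, oil and a snack, would have scored.

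Two further consequences follow. The background section presents the pilot as the basis for larger trials, and a larger trial needs to know whether the two programs actually produce different diets. Without that, a null result on weight gain or biomarkers could mean that the diet has no effect or that the arms ate alike. Also, the Analytical Plan's general between-group tests, if applied to adherence as collected, would compare scores from two different forms. The text gives no support for treating the cut-offs as equivalent across them.

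**Working it through.** **No planned figure to reproduce.** The protocol sets 60 women, 30 per arm, and states that no sample size was calculated. The first check is a count of the scores the plan would produce.

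| MedDiet form | Enrollment | 20-24 wk | 26-30 wk | 34-38 wk |
|---|---|---|---|---|
| MedDiet arm (30) | 0 | 30 | 30 | 30 |
| Control arm (30) | 0 | 0 | 0 | 0 |

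At full retention that is 30 × 3 = 90 forms, none before the program starts and none in controls.

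**Delay to the first score.** Enrollment runs from 6 0/7 to 16 6/7 weeks. Shortest delay: 20 0/7 − 16 6/7 = 3.1 weeks. Longest: 24 0/7 − 6 0/7 = 18.0 weeks.

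**What the plan can estimate.** Assume 18 of 30 MedDiet women score 12 or more. The exact (Clopper-Pearson) 95% CI for 18/30 = 60% is 40.6% to 77.3%.

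**What it leaves open.** The same 60% fits very different contrasts, depending on the unmeasured control rate (assumed values, Newcombe 95% CI):

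| Controls scoring ≥12 | Difference (points) | 95% CI |
|---|---|---|
| 3/30 (10%) | +50 | 26 to 67 |
| 9/30 (30%) | +30 | 5 to 50 |
| 18/30 (60%) | 0 | −23 to 23 |

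**Precision if both arms complete the MedDiet form.** The 95% CI half-width for the difference in mean score, in SD units, is t(0.975, 2n−2) × √(2/n) × √(1−ρ²). Here n is the number scored per arm and ρ is the assumed correlation between the enrollment and later scores.

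- n = 30: 2.002 × 0.2582 = 0.517 without adjustment; × √(1−0.25) = 0.448 at ρ = 0.5; × √(1−0.49) = 0.369 at ρ = 0.7.
- n = 25 (assumed loss): 2.011 × 0.2828 = 0.569 without adjustment; 0.493 at ρ = 0.5 (rounded from 0.4925); 0.406 at ρ = 0.7.

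**Does any other text fill the gap?** The joint wording in Outcomes refers back to the earlier description, which is of two arm-specific forms. Each is scored against its own recommended guidelines, so a 12 on one need not mean a 12 on the other. The FIGO checklist is completed at baseline only. No rule converts the enrollment questionnaire or the recall into a MedDiet score. The photos concern six delivered meals per three weeks, and those meals differ by arm.

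**The case against.** The strongest reply is that the objective is answered as written. It concerns adherence to the MedDiet program and names no comparator, whereas the secondary objectives state their between-group comparisons outright. Measuring each arm against its assigned diet is a legitimate feasibility construct; a MedDiet score in controls measures dietary similarity rather than their adherence. This stands in part: the level is estimable and should be kept. It does not supply a reference for calling adherence raised, or a contrast for crediting the program.

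Second, controls also receive free home-delivered meals, so a between-arm contrast would compare one supplied, counselled package with another. It would not isolate the effect of free delivery. That is correct, and the proposed estimate should not be read that way.

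Third, the appendices are not in the documents, so items in the enrollment questionnaire or the trimester forms might overlap with the MedDiet form. The reference to counselling sessions in Outcomes might also loosely include the baseline session. Neither can be excluded, but the Baseline Visit list and the schedule table do not place the form there, and no text uses other items to score adherence.

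Fourth, no adherence test is actually planned, so the risk of comparing two scales is conditional. That is accepted.

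Finally, repeated MedDiet items may prompt controls to eat that way. This is a real cost. The enrollment score avoids most of it and is the better-supported half of the change.

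**Conclusion.** The concern holds and should be fixed. Followed as written, the plan gives 0 of 60 enrollment scores and 0 of 30 control scores on the MedDiet scale. It can report the MedDiet arm's level from 20-24 weeks onward. It cannot report a change from enrollment, a difference between arms, or MedDiet uptake in controls on that scale. Those counts and the 3-to-18-week delay come directly from the documents.

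The intervals are illustrations that rest on assumed response rates, correlations and retention. They show that one observed level is compatible with a large between-arm difference or none, and that the existing sample would estimate the difference to within about 0.4 to 0.6 SD if the data were collected. The pilot remains valid as a description of adherence in the MedDiet arm.

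**What to change.** - Give the MedDiet questionnaire (Appendix S/T) to all women after consent and before the allocation envelope is opened, then to both arms at 20-24, 26-30 and 34-38 weeks. Keep the routine-diet questionnaire as an additional control-arm measure.
- For feasibility, keep the percentage of MedDiet-arm women with high adherence, with an exact 95% CI, at one named time point.
- Add the between-arm difference in the continuous MedDiet score at that same time point, adjusted for enrollment score and BMI category, with a 95% CI. The 26-30 week session is a natural choice because all women also have blood drawn then.
- State that routine-diet scores or categories will not be tested against MedDiet scores or categories.
- Use meal photos only as a supportive measure of meal uptake.

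**Cost.** Full collection is 60 × 4 = 240 MedDiet forms against 90 planned, so 150 extra: 60 at enrollment and 30 × 3 = 90 in controls. The form already exists in English and Spanish and the sessions are already scheduled, so no new visit, staff or translation is needed. The form should be short: the reference list describes the source screener as 14 items, although the length of the modified version is not shown. Expect a few minutes per session. The schedule, Outcomes and Analytical Plan need rewording.

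Two limits remain. The items may prompt MedDiet eating in controls, which would shrink the difference, and the follow-up scores are self-reported by women who know their allocation. An enrollment score cannot be recovered once a woman has started the program, so the change should be made before further enrollment.

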Participants will be randomized to a MedDiet program or the currently offered American College of Obstetricians and Gynecologists (ACOG)-based dietary counseling program at Myers Park and North Park OBGYN Clinic(s) in Charlotte, North Carolina.

Duration of Study and Participating Site

This will be a multi-center study including Myers Park OB/GYN Clinic and North Park OB/GYN Clinic which are academic obstetrical practices providing prenatal care to a socially vulnerable and highly racial/ethnic diverse population. All new scheduled prenatal visits will be screened in Epic for eligibility by our research team.

We anticipate full completion of the study by July 2025.

Study population (Table 1)

Inclusion Criteria	Exclusion Criteria

• Viable singleton pregnancy in the first trimester (6 0/7- 16 6/7 weeks); includes twins reduced to singleton spontaneously or vanishing twin syndrome• BMI $\geq 25.0 \text{ kg/m}^2$; calculated by dividing maternal weight in kilograms by height in meters squared using a calibrated scale and standard metric measure (BMI calculator available at www.cdc.gov)• Confirmed intrauterine pregnancy by ultrasound exam (6-16 weeks)• Age 18 years or older• Primary language of English or Spanish	
• BMI $< 25.0 \text{ kg/m}^2$• Known pre-pregnancy diabetes• Hemoglobin glycosylated (A1C) $> 5.7\%$ at first prenatal visit• Pre-pregnancy hypertensive disease• Non-viable pregnancy• Known allergies to an essential component(s) of MedDiet• Inability to read or write in primary language• Mental incapacity to make medical decisions• Food insecurity

Sample Size

Since this is a pilot study, we aim to enroll 60 participants with 30 per study arm. Based on the patient population at Myers Park, we anticipate the following racial/ethnic breakdown of subjects.

Table 2 Anticipated Enrollment (all subjects will be female)

Race	Non-Hispanic	Hispanic	Total
Asian	1	0	1
Black or African American	15	0	15
White	6	36	42
More than One Race	2	0	2
Total	24	36	60

Methods and Intervention

- Fig 1 and Table 3 provide a detailed view of the study activities.
- With the purpose of overcoming language barriers, the dietary program was developed in English and Spanish. Multiple aids were created including practical educational tools, recipes, shopping list, and meal portion guidance to improve engagement and enhance sustainability.

Randomization and Study Groups:

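### Advice at the later sessions to increase exercise depends on contraindications found at the 6-16 week baseline visit, and no visible text says the check is repeated (minor, cheap to correct)

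*Combined protocol and SAP*

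**What the plan says.** The protocol gives exercise advice in two places and sets a different condition in each.

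- **Baseline Visit.** The condition is current status: "If there are no clinical contraindications, women will be encouraged to start with low intensity, short periods of exercise". The advice is only to begin gently.
- **Trimester Visits.** At the three later sessions the advice is to do more, for longer and harder, until delivery. The condition looks back: "If no clinical contraindications were established during the baseline visit, subjects will be encouraged to gradually increase their length and intensity of physical activity". The same bullet limits this to what the woman tolerates and cites ACOG recommendations.

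On timing, the baseline session is placed as follows: "This will occur during their initial prenatal visit at 6-16 weeks of pregnancy". The inclusion criteria in Table 1 give the exact limits: "Viable singleton pregnancy in the first trimester (6 0/7- 16 6/7 weeks". The later sessions need not be face to face; the text allows "in-person, virtual, or phone call dietary counseling sessions will be scheduled at the following time points", namely 20-24, 26-30 and 34-38 weeks.

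The schedule of activities (the first of two tables numbered 3) marks diet and physical activity counseling at all four time points in both arms. It marks medical, reproductive and obstetric history at enrollment only. It has no row for a contraindication check.

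**The concern.** A condition on safety advice should describe the woman as she is when the advice is given. The baseline wording does that. The later wording, which governs the stronger advice, points to a visit that may be months past.

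The trial expects new conditions to appear. Known pre-pregnancy diabetes and pre-pregnancy hypertensive disease are exclusions, while hypertensive disorders of pregnancy, gestational diabetes and preterm birth are among the adverse pregnancy outcomes to be examined. A visit at 6-16 weeks could not have established a complication that had not yet arisen. Whether any of these limits exercise is for the obstetric team; the protocol does not say.

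The stake is participant safety, and it is small. The protocol does not say who runs the later sessions. Whoever does is directed to the baseline finding, although the study already collects current complications from the medical record.

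**Working it through.** The protocol gives no figure on this point, so there is none to reproduce. The check has two parts: how old the baseline finding is when it is used, and whether any other provision renews it.

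**Age of the check at each session**

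Inputs: baseline from 6 0/7 to 16 6/7 weeks (Table 1), that is 6.00 to 16.86 weeks; session windows of 20-24, 26-30 and 34-38 weeks (Trimester Visits).

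Shortest gap = start of window − 16.86. Longest gap = end of window − 6.00.

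| Session | Shortest gap (weeks) | Longest gap (weeks) | Longest gap if the window runs to 6/7 of its last week |
|---|---|---|---|
| 20-24 weeks | 20 − 16.86 = 3.1 | 24 − 6 = 18 | 24.86 − 6 = 18.9 |
| 26-30 weeks | 26 − 16.86 = 9.1 | 30 − 6 = 24 | 30.86 − 6 = 24.9 |
| 34-38 weeks | 34 − 16.86 = 17.1 | 38 − 6 = 32 | 38.86 − 6 = 32.9 |

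The last column reads the session windows as the enrollment limit is written. These figures show only how dated the condition is. The documents give no basis for counting how many women would develop a contraindication after baseline, so no count is offered.

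**Does another provision renew the check?**

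- *Blood pressure and heart rate* are taken at prenatal visits across all trimesters (Outcomes, Cardiovascular parameters). They are collected for trend comparison and are not tied to the exercise advice.
- *Routine prenatal care* continues. Supplies, for example, are handed out "during their routine 26-30 week prenatal visit", so a phone session in that window does not mean the woman goes unseen. No link to the advice is written.
- *Medical-record data* include "Current pregnancy, scans, complications, progress reports, clinic reports, hospital reports", and the schedule marks pregnancy data collection in every window. They are gathered as study data.
- *Session instruments* are the "Trimester Collection Form (Appendix EE-GG"), the Diet and Physical Activity Recall (Appendix CC/DD) and, in the schedule, a general assessment questionnaire. Their content is not shown.
- *Adverse pregnancy outcomes* follow clinic guidelines, and the principal investigator monitors safety. Neither provision mentions exercise advice.

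Each item lowers the practical risk. None, as visible, changes the dated condition.

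**Two readings of the clause**

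- Literal: a woman with no contraindication at baseline and one at 30 weeks meets the condition and is encouraged to increase.
- Softer: the clause only carries the baseline exclusion forward. The text is then silent on new contraindications.

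On either reading, no current check is stated for the stronger advice.

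**The case against.** The strongest reply is that the gap may not exist. The Trimester Collection Form and the activity recall are completed at these same sessions and are natural places for a question on current status. The ACOG opinion that the advice follows may also deal with contraindications arising later. None of the three can be seen, so silence in the visible text is weak evidence that nothing is there. This stands as a limit on the finding, and the remedy allows for it.

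A second reply is that the literal reading is unnatural: nothing tells staff to ignore a new complication, and the advice is limited to what the woman tolerates. That is fair as a guess at intent. But tolerance governs how much she does, while a contraindication governs whether she should be encouraged at all. An explicit condition with the wrong date is a different fault from a missing detail.

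A third reply is that the trial's results are untouched. This is correct. The clause is the same in both arms, is not the randomized intervention, and enters no outcome definition or analysis.

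Finally, a chart check does not ask the woman about new symptoms, which matters most by phone. That is a reasonable limitation of the fix, and the obstetric team can add such a question.

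**Conclusion.** The concern holds as a minor point of participant-safety wording. The condition for advising more exercise refers to a visit 3.1 to 32 weeks earlier (up to 32.9 if the last window runs to its final day), whereas the baseline advice rests on current status. No visible text states that the check is repeated.

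Harm is unlikely given concurrent prenatal care and the other provisions listed above. The conclusion assumes that the unseen forms and the cited ACOG opinion do not already supply the check; if they do, only a cross-reference is missing. It is no evidence that participants lack safety oversight, and it has no bearing on bias, sample size or analysis.

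**What to change.** In Trimester Visits, replace the opening condition of the exercise bullet with: *If no clinical contraindications are present at that session (per current EPIC record)*. This restores the present-tense condition used at baseline and works for in-person, virtual and phone sessions. Which conditions count, and what advice follows, stays with the obstetric team. If the Trimester Collection Form already asks, cite it in this sentence instead of adding a second check.

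The cost is one clause, with no extra visit or test, plus a brief look at the chart each time: 60 women × 3 sessions = 180 looks. At an assumed 1-3 minutes each, that is 180 × 1 min = 3 hours to 180 × 3 min = 9 hours of staff time over the trial, or 1/20 to 3/20 (5-15%) of a session of about 20 minutes. It is less if combined with the record collection already scheduled in each window.
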